10.7. Missing/Partial Dates at Screening Visits

The following rules apply to dates recorded during the screening visits (eg, prior anticancer therapy).

- 1) Missing day only
 - The first day of the month will be used.
- 2) Missing day and month
 - If the year is the same as the year of the earliest inform consent date at screening, the 1st of January will be used.
 - If the year is before the year of the earliest inform consent date at screening, the 15th of June will be used.
- 3) Missing day, month and year
 - No imputation will be applied.

If the imputed end date is before the start date, the start date will be used as the end date. If the imputed dates are after the inform consent date at screening, then the inform consent date will be chosen.

11. CHANGES TO ANALYSES SPECIFIED IN THE PROTOCOL

Below is a summary of changes to the analyses specified in the protocol:

- Pharmacokinetic Analysis Set (PAS) as well as PK-related analyses are not described here and will be in a stand-alone PK/pharmacodynamic report.

12. APPENDICES

12.1. Appendix A: Best Overall Response Confirmation Rule

CR CONFIRMATION:

To confirm a CR (the first CR), another CR (the confirming CR) at least 4 weeks after the first CR will be looked for. It is required that there is no other overall response, except CR or NE or NA, between the first CR and the confirming CR.

- If such confirming CR exists, then the subject BOR is confirmed CR.
- If such confirming CR is guaranteed non-existing (eg, the first CR followed by PD or off-study), then the confirmed BOR is SD if the first CR was assessed ≥ 38 days after the randomization date, otherwise the first CR will be replaced by UNK and the BOR will be derived subsequently.

PR CONFIRMATION:

To confirm a PR (the first PR), another CR or PR at least 4 weeks after the first PR will be looked for. It is required that there is no other overall response, except CR or PR or NE or NA, between the first PR and the confirming CR or PR.

- If such confirming CR or PR exists, then the subject's BOR is PR (confirmed).
- If such confirming CR or PR is guaranteed non-existing (eg, the first PR followed by PD or off-study), then the confirmed BOR is SD if the first PR was assessed ≥ 38 days after the randomization date, otherwise the first PR will be replaced by UNK and the BOR will be derived subsequently.

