12.7.2.3. Objective Response Rate

For the secondary efficacy endpoints of ORR, DOR, and TTR, analyses will be performed using Investigator- and IRC-assessed response.

Objective response rate is defined as the rate of confirmed CR and PR per RECIST v1.1.

A summary of best objective response by arm will be produced. A Cochran-Mantel-Haenszel (CMH) test will be used to compare ORR between the 2 treatment arms. A logistic regression model may be used to estimate the treatment effect in terms of an odds ratio. The odds ratio and its associated 95% CIs will be presented.

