8.2. Objective Response Rate (ORR)

Objective response rate will be derived from BOR. Best overall response is defined as the best time point response that a subject achieves during the course of the study, with the response ranked according to the following order (from best to worst): CR>PR>SD>PD>UNK>Other (including Not Evaluable and Not Assessed). The number and proportion of ITT subjects with each category of BOR will be presented by treatment arms.

Per RECIST v1.1, SD that occurred within <38 days from the randomization date is assigned as UNK (6 weeks minus 5 days per protocol allowed visit window). In addition, the BOR of CR or PR requires a confirmation scan. The specific confirmation rule can be found in [Appendix A: Best Overall Response Confirmation Rule](#).

The estimated ORR (percent of subjects with a BOR of CR or PR) and a 2-sided 95% CI (via exact binomial) will be provided by treatment arms. All subjects in the analysis set will be included in the denominator in the calculation of the percentage for each response category or ORR. If the subject has no response assessment, it will be treated as a non-responder in the analyses.

Objective response rate will be analyzed using one-sided Cochran-Mantel-Haenszel (CMH) test (see Appendix B: One-Sided Cochran–Mantel–Haenszel (CMH) Test) to compare the two treatment arms. The odds ratio and its 95% CI will be estimated. The strata will be those used for stratified randomization. If the number of responders in each arm is low ($n < 5$), Fisher exact test will be used instead. The odds ratio (unstratified) and its 95% exact CI will be estimated.

In addition, the ORR (and BOR) without confirmation per IRC as well as per Investigator assessments will be analyzed similarly.

The waterfall plots of the maximum % reduction from baseline in target lesion measurement (sum of diameters) will be presented by treatment arms. The target lesions post-baseline vs. baseline have to be matched in order to calculate % change, except for the case where lesions disappeared (*Absent* or *Too Small to Measure*) or merged or split. If the lesion status is “Absent,” 0 mm will be used as the measurement; if the lesion status is “too small to measure,” 5 mm will be used per RECIST v1.1 guidance.

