8.4. Multiple Comparisons/Multiplicity Adjustment

Of the secondary endpoints, OS and ORR are designated as key secondary efficacy endpoints. The primary and key secondary endpoints will be tested at an overall one-sided Type I error rate at 2.5% level based on the fixed sequence testing procedure at the time of primary analysis. These endpoints will be tested in the following order:

- PFS based on IRC
- OS
- ORR based on IRC

In addition, a hierarchical testing procedure will be adopted for OS analyses only if the primary efficacy endpoint PFS is statistically significant. Two analyses are planned for OS: 1) an interim analysis at the projected time of the final analysis for PFS (provided PFS is significant); 2) a final analysis for OS when 150 deaths are observed. Overall survival at the interim will be tested with the alpha being determined using the gamma spending function ($\gamma = -8$), and the overall Type I error rate will be controlled at the 1-sided 0.025 level. The log-rank test stratified by randomization stratification factor will be used to compare OS between the two treatment arms.

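### Read literally, SAP Appendix A tests confirmation only for the first CR and first PR, so PR-SD-PR-PR counts as a non-responder; and it states no precedence where its CR and PR rules disagree

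*SAP*

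**What the plan says.** Protocol 12.7.2.3 fixes the endpoint: "Objective response rate is defined as the rate of confirmed CR and PR per RECIST v1.1". SAP 8.2 builds ORR from best overall response: "Best overall response is defined as the best time point response that a subject achieves during the course of the study", ranked CR over PR over SD. It then adds "In addition, the BOR of CR or PR requires a confirmation scan" and sends the reader to Appendix A for the rule. SAP 8.4 gives the endpoint its standing: "Of the secondary endpoints, OS and ORR are designated as key secondary efficacy endpoints", with IRC ORR third in the fixed sequence after IRC PFS and OS.

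Appendix A has one rule for CR and one for PR. The PR rule reads "To confirm a PR (the first PR), another CR or PR at least 4 weeks after the first PR will be looked for" and requires "no other overall response, except CR or PR or NE or NA, between the first PR and the confirming CR or PR". If a confirming scan is found, the subject is a confirmed PR. If not, "If such confirming CR or PR is guaranteed non-existing (eg, the first PR followed by PD or off-study), then the confirmed BOR is SD", provided that the first PR was at least 38 days after randomization. A first PR before day 38 is instead set to UNK and the best response is worked out again. The CR rule has the same structure, except that only a CR can confirm a CR.

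SAP section 11 lists no change to the protocol's definition of ORR.

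**The concern.** There are two separate problems.

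**Later pairs are not tested.** Once an SD follows the first PR, that PR can never be confirmed, because any later PR or CR would have the SD in between. The fallback then sets the subject's result to SD, and nothing tells the programmer to look at responses after the SD. A subject can therefore have two consecutive PRs that satisfy the 4-week gap and the rule on intervening responses, and still be a non-responder. Protocol Appendix 15.9 (Table 6) allows PR followed by SD when shrinkage slips below 30% without reaching the PD criterion.

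**The two rules can disagree.** Where a record contains both a PR and an unconfirmed CR, the PR rule may return confirmed PR while the CR rule returns SD. Appendix A does not say which prevails, so two programmers could report different results.

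At stake is the responder count in an alpha-controlled endpoint with few expected responders. SAP 8.6 restricts DOR to confirmed responders, so DOR would omit the same subjects.

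**Working it through.** The plan gives no target, rate or power for ORR, so there is no planned figure to reproduce.

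**1. Appendix A applied to response records.** Assume scans every 6 weeks. Then every scan is past day 38 and every gap exceeds 4 weeks. Three readings:

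- A: only the first CR and the first PR are tested; the better result is kept by the 8.2 ranking.
- B: as A, but the CR rule is final whenever a CR occurs (a precedence the SAP does not state).
- C: any CR or PR may open a confirming pair; the best result is kept.

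| Record | A | B | C |
|---|---|---|---|
| PR-SD-PR-PR | SD | SD | PR |
| PR-CR-PD | PR | SD | PR |
| SD-PR-PR | PR | PR | PR |
| PR-NE-PR | PR | PR | PR |

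Take all four-scan records with CR, PR or SD at scans 1 to 3 and CR, PR, SD or PD at scan 4: 3 × 3 × 3 × 4 = 108. Reading A loses three that C counts as responders: PR-SD-PR-PR, PR-SD-PR-CR and CR-SD-CR-CR. Reading B loses 33. These are counts of patterns, not probabilities.

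**2. The day-38 boundary.** Suppose the first PR falls 37 days after randomization and is followed by SD, PR, PR. It is set to UNK, the result is derived again, and the later pair gives confirmed PR. With the first PR at day 42, the same record gives SD.

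**3. How many subjects.** Simulation of the AG-120 arm (n = 124). All inputs except the scan schedule and the 6-month median PFS are assumptions:

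- scans every 42 days for eight scans, then every 56 days; exponential PFS with median 6 months;
- plateau tumour change normal with mean 0 or −5% and SD 22%, reached by week 12;
- measurement error with SD 3% to 10% on the sum of diameters.

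The share lost is (subjects with an adjacent PR pair whose first PR is not followed by a PR) ÷ (subjects with any adjacent PR pair).

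- Without a PD rule measured from the smallest sum: about 5% to 14% of confirmed responders, or 0.3 to 1.6 subjects.
- With the Table 6 PD rule (at least 20% and 5 mm above the smallest sum; baseline sum of 80 mm assumed): about 5% to 8%, or 0.4 to 0.8 subjects.

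The second result is the better guide, because the first counts as SD some swings that the protocol would call PD.

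**4. What one subject does to the test.** One AG-120 subject is 1/124 = 0.8 percentage points of ORR. The only response rate in the documents is 3 of 38 (Protocol 5.3.3.1). Applied to 124, it gives 3/38 × 124 = 9.8, about 10 responders. Assume 0/62 on placebo. SAP 8.2 plans a CMH test, with Fisher's exact test when responders are few, so both are shown. For CMH, Appendix B is used with a single stratum: Z = (O − E11)/√V, V = E11 × E22/(N − 1), N = 186. At 8 responders E11 = 124 × 8/186 = 5.33, E22 = 62 × 178/186 = 59.33, V = 1.71 and Z = 2.04.

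| AG-120 responders | Fisher, one-sided p | CMH, one-sided p |
|---|---|---|
| 10 | 0.0153 | 0.0109 |
| 9 | 0.0235 | 0.0151 |
| 8 | 0.0361 | 0.0207 |
| 7 | 0.0552 | 0.0286 |

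The 0.025 line falls between 9 and 8 responders for Fisher and between 8 and 7 for CMH. With 1/62 on placebo, Fisher gives 0.0691 at 10 responders and needs 13 (0.0233).

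**The case against.** **The word first may only be a label.** It could distinguish the earlier from the later scan of any pair. The two examples given for the SD fallback, PD and leaving the study, are both terminal, and PR-SD-PR-PR is neither. SAP 8.2 and Protocol 12.7.2.3 also fit a rule that accepts any pair. This reading is possible. It sits badly with a fallback that fixes the whole subject's result, and with re-derivation written only for responses before day 38. It means that misclassification follows from the literal text, but not that the programmer is certain to apply it so.

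**PR-CR-PD and CR-PR-PR.** A reader might infer that these subjects are also lost as responders. The documents do not support that. The PR rule accepts a CR or a PR as the confirming scan, so it returns confirmed PR in both cases, and the 8.2 ranking puts PR above SD. Only the missing precedence remains. Records that regress from CR should also be rare: after non-nodal target lesions disappear, 5 mm of regrowth already meets the Table 6 PD criterion.

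**Size.** A reader might infer a loss of two or more subjects. That needs high assumed measurement error without the PD rule, or a median PFS longer than the planned 6 months.

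**Consequence.** The loss falls mainly on AG-120, where most responders are expected, so it is conservative. ORR is tested only after OS, which has 64% power at the assumed HR of 0.67, and Protocol 12.7.2.1 itself doubts that OS is adequately powered given cross-over. SAP 8.2 also plans ORR without confirmation, in which these subjects count as responders. All of this stands and limits the importance of the point. The unconfirmed analysis, however, is supportive and does not correct the endpoint in the testing sequence.

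**Conclusion.** The point holds in two parts. First, on the literal text of Appendix A, PR-SD-PR-PR (likewise PR-SD-PR-CR and CR-SD-CR-CR) is a non-responder despite a later pair that meets the appendix's own standard. This conflicts with Protocol 12.7.2.3 and SAP 8.2. Second, for PR-CR-PD and CR-PR-PR the two rules return different answers and no precedence is stated; the 8.2 ranking favours confirmed PR.

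The expected effect is probably about one AG-120 subject of 124 or fewer at a 6-month median PFS. That rests on assumed tumour-change and measurement-error distributions, since the plan gives none. The direction is against AG-120, so the rule would not be expected to create a false claim of benefit. It can matter only if the ORR test is reached and the count is near the threshold, where one or two subjects decide the result. The threshold counts assume the Phase 1 rate on AG-120 and 0/62 or 1/62 on placebo. It should be corrected because the rule gives a wrong result in a key secondary endpoint and the repair is cheap.

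**What to change.** Amend Appendix A before database lock:

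- Apply the confirmation test to every CR and every PR, not only the first of each. Keep the 4-week minimum and the present lists of permitted intervening responses.
- Take the subject's confirmed best response as the best result over all eligible scans, by the 8.2 ranking.
- Count an unconfirmed CR or PR at day 38 or later as SD only if no pair in the record confirms.
- State that a CR not confirmed as CR can still count toward a confirmed PR. This settles PR-CR-PD and CR-PR-PR.
- Derive DOR for the same responders, starting from the first scan of the confirmed pair.

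If the sponsor already intends that any pair may confirm, the same wording makes that explicit. The cost is SAP text and one derivation step; no new data are needed.

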12.2. Appendix B: One-Sided Cochran–Mantel–Haenszel (CMH) Test

The Cochran–Mantel–Haenszel (CMH) test compares binary responses of two treatment groups, adjusting for stratification factors. In the CMH test, the data are arranged in a series of associated

2×2 contingency tables, the null hypothesis is that the observed response is independent of the treatment used in any 2×2 contingency table.

Let O_{hij} be the observed frequency of treatment i ($i=1$ or 2) with outcome j ($j= 1$ or 2) in stratum h and E_{hij} be the expected frequency of treatment i ($i=1$ or 2) with outcome j ($j= 1$ or 2) in stratum h , where

$$E_{hij} = \frac{(O_{hi1} + O_{hi2}) \cdot (O_{h1j} + O_{h2j})}{O_{h11} + O_{h12} + O_{h21} + O_{h22}}$$

Also, let P_{hij} be the probability of outcome being j given treatment being i ($i=1$ or 2 , $j= 1$ or 2) in stratum h . To test the following hypothesis,

$$H_0 : P_{h11} = P_{h21} \text{ for all } h \in \{1, \dots, H\}$$

versus

$$H_1 : P_{h11} > P_{h21} \text{ for at least one } h \in \{1, \dots, H\}$$

The one-sided Cochran-Mantel-Haenszel Test Statistics is constructed as:

$$Z_{CMH} = \frac{\sum_{h=1}^H (O_{h11} - E_{h11})}{\sqrt{V_{11}}} \sim Z$$

Where

$$V_{11} = \text{Var}\left(\sum_{h=1}^H (O_{h11} - E_{h11})\right) = \sum_{h=1}^H \frac{E_{h11} \cdot E_{h22}}{O_{h11} + O_{h12} + O_{h21} + O_{h22} - 1}$$

The test statistic Z_{CMH} will be compared with standard normal distribution to obtain p-value of the CMH test.

12.3. Appendix C: Overall Survival Analyses using Rank Preserving Structural Failure Time Model (RPSFT)

Subjects who received placebo per randomization is allowed to crossover and receive AG-120 upon radiographic PD. To account for the potential bias introduced by crossover, the RPSFT model (Robins and Tsiatis, 1991; White et al, 1997 & 1999) is utilized as a sensitivity analysis.

The RPSFT model and assumptions

RPSFT assumes that the AG-120 after the switch is acting by multiplying survival time by a given factor (acceleration factor) relative to placebo, and assumes the treatment effect is the same for all subjects regardless of when treatment is received (common treatment effect).

Specifically, let U_i denote the latent survival time if subject i were assigned to the placebo arm, adhere to it and discontinue only after the event (also called counter-factual event time),

$$U_i = T_i^{off} + T_i^{on} \exp(\psi_0)$$

where T_i^{off} is the time that subject i is off treatment, and T_i^{on} is the time that subject i is on treatment; $\exp(\psi_0)$ is the acceleration factor which denotes the amount by which a subject's survival time is 'increased' by the active treatment. A positive (negative) ψ_0 value corresponds to a harmful (beneficial) treatment effect. Specifically, for

- AG-120 subjects at randomization: $U_i(\psi_0) = T_i^{ag120} \exp(\psi_0)$;
- placebo subjects who crossed over to AG-120: $U_i(\psi_0) = T_i^{pbo} + T_i^{ag120} \exp(\psi_0)$;
- placebo subjects without crossover: $U_i(\psi_0) = T_i^{pbo}$.

In order to estimate ψ_0 , we assume that U_i is independent of randomized treatment assignment and can be viewed as baseline characteristics. Thus, if we conduct a hypothesis test (such as log-rank test) for the treatment difference on $U_i(\psi_0)$, we shall obtain a p-value close to 1 with a sufficiently large sample size. RPSFT works by reconstructing the survival time of subjects, as if they have never received active treatment. A grid search within a reasonable range will then be performed in order to find the estimated ψ_0 with the largest p-value. The corresponding point estimate of HR between the two arms will be reported, with the 95% CI generated from bootstrapping method.

Re-censoring

Administrative censoring refers to the censoring where the event is not observed by the time of data cutoff. Unfortunately its time scale cannot be adjusted in the same way as event, as potential bias could be introduced because censoring would be dependent on time spent on treatment and thus treatment arm (informative censoring). To overcome this problem, the counter-factual event times are re-censored by the minimum U_i that could have been observed for individuals (with and without events) across their possible treatment changes.

Let C_i be the potential censoring time for a subject i . The subject is then re-censored at the minimum possible censoring time:

$$D_i^*(\psi_0) = \min(C_i, C_i \exp(\psi_0)).$$

If $D_i^* < U_i$, then U_i is replaced by D_i^* and the subject is censored. For treatment arm where switching didn't occur, re-censoring is not applied.

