9.7. Study Treatment Preparation and Administration

Daily treatment with AG-120 or placebo will begin on C1D1; clinical observations will be conducted over 4 hours following the first dose of study treatment on C1D1. Dosing is continuous; there are no planned inter-cycle rest periods. Subjects should be instructed to take their QD dose at approximately the same time each day.

Subjects should be instructed to swallow tablets whole and to not chew the tablets. Subjects may take AG-120 or placebo tablets with or without food. Subjects should be advised that if AG-120/placebo tablets are taken with food, the subject should avoid grapefruit or grapefruit products and avoid consuming a high-fat meal. Please refer to examples of low-fat and high-fat meals in Appendix 15.7.

If the subject forgets to take the daily dose, then they should take AG-120 or placebo within 12 hours after the missed dose. If more than 12 hours have elapsed, then that dose should be omitted, and the subject should resume treatment with the next scheduled dose.

Subjects will continue to receive best supportive care throughout the study, regardless of treatment arm.

Subjects may continue with their assigned study treatment until disease progression, development of unacceptable toxicity, confirmed pregnancy, death, withdrawal of consent, the subject is lost to follow-up, or the Sponsor unblinds or ends the study, whichever occurs first. Subjects who are determined to be on AG-120 upon study unblinding may continue on AG-120. For subjects who are determined to be on AG-120 upon radiographic disease progression and have demonstrated clinical benefit, PIs, with consult from the Sponsor, may keep the subjects on AG-120 after the disease progression. (See Section 9.6 for additional unblinding scenarios.)

9.8. Criteria for Dose Modification, Discontinuation of Study Treatment, Continuation Beyond Radiographic Progression, and Allowance of Palliative Radiotherapy

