8.3. Overall Survival (OS)

The OS analysis will be based on ITT set and will include all OS data, including data after crossover.

Overall survival is defined as the time in months from the randomization date to the date of death due to any cause. Subjects without documentation of death at the time of the data cutoff for analysis will be censored at the date the subject was last known to be alive, or the data cutoff date, whichever is earlier. The last known alive date is the last record in the study database. For example, this date may be the maximum of the last visit date or last contact date, including telephone follow-up where the subject is known to be alive.

As a primary analysis, a stratified one-sided log-rank test will be used to compare OS between the two treatment groups, with the one-sided significance level controlled at 0.025. The HR along with the 95% CI will be estimated using a stratified Cox model. For both the stratified log-rank test and the stratified Cox model, the strata will be those at randomization. A Kaplan-Meier plot for OS will be presented by treatment arm. Estimates and 95% CIs for the 25th percentile, median, and 75th percentile for OS will be presented by treatment arm (if estimable). Probabilities of survival at selected time points (3 months, 6 months, 9 months, and 12 months) may also be presented.

In addition, the following subgroup analyses will be performed:

- Subgroup analysis with unstratified log-rank test and unstratified Cox regression model. The HR (AG-120/placebo) with its 95% CI will be displayed for all subgroups graphically in a forest plot. The subgroups will include:
 - The actual number of prior line of therapies in advanced setting (1 vs. ≥ 2)
 - Gender (female vs. male)
 - Extent of disease at screening (locally advanced vs. metastatic)

- If subject had both locally advanced and metastatic, it would be considered as metastatic
- Intrahepatic vs. extrahepatic
 - Perihilar will be lumped into extrahepatic category
- ECOG at baseline (0 vs. ≥ 1)
- Regions (North America vs. Europe vs. Asia)

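### SAP Appendix C defines time on treatment one way and uses it another: as defined, its RPSFT lines discard survival after AG-120 stops, which can make the crossover-adjusted OS hazard ratio look too favourable

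*SAP*

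**What the plan says.** SAP Appendix C gives a general formula, U = T_off + T_on·exp(ψ), "where T_i^{off} is the time that subject i is off treatment, and T_i^{on} is the time that subject i is on treatment". It then specialises the formula in three lines:

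- AG-120 arm ("AG-120 subjects at randomization"): U = T_ag120·exp(ψ)
- placebo, crossed over: U = T_pbo + T_ag120·exp(ψ)
- placebo, not crossed over: U = T_pbo

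T_ag120 and T_pbo are never defined. A positive ψ is labelled harmful. The reported result is the hazard ratio at the ψ with the largest p-value, with a bootstrap interval. In an arm without switching, "re-censoring is not applied". The grid-search test is described only by example: "if we conduct a hypothesis test (such as log-rank test) for the treatment difference".

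On treatment duration, Protocol 9.7 says: "Subjects may continue with their assigned study treatment until disease progression", with other stopping reasons, and lets some subjects stay on AG-120 after progression. For the main OS analysis, SAP 8.3 says that "a stratified one-sided log-rank test will be used to compare OS between the two treatment groups", on the ITT set and including data after crossover. SAP 8.3 says that RPSFT will be explored, and Appendix C calls it a sensitivity analysis.

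**The concern.** The AG-120 and crossover lines follow from the general formula only if every subject takes AG-120 until death or censoring. The treatment rules and the planning medians say otherwise. A programmer therefore has two readings, and each breaks something:

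- If T_ag120 is time on drug, as the stated definition implies, survival after the last dose disappears from U.
- If T_ag120 runs from first AG-120 dose to death or censoring, the lines are coherent but contradict the stated definition of T_on.

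Protocol 12.7.2.1 expects crossover to prevent the true survival effect from being measured, and RPSFT is the only adjustment specified in detail. If its key quantity is left open, the choice between materially different adjusted hazard ratios could be made after unblinding.

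**Working it through.** **Planning inputs.** OS medians are 8 vs 12 months, PFS medians 3 vs 6 months, with 150 OS events, 2:1 allocation and one-sided alpha 0.025 (SAP Section 5). The stated OS power reproduces: √(150 × 1/3 × 2/3) × |ln 0.67| − 1.96 = 5.774 × 0.4005 − 1.96 = 0.352, and Φ(0.352) = 63.8%, against a stated 64%. The documents give no RPSFT figure to reproduce.

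**Three readings.** Let S be time before AG-120, *on* the time on AG-120, and *off* the survival after it stops. Observed survival is T = S + on + off.

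- General formula: U = S + off + on·exp(ψ)
- Start-to-death: U = S + (on + off)·exp(ψ)
- Dosing time only (the three lines with the stated definition): U = S + on·exp(ψ)

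At ψ = 0 the first two return T. The third returns T − off, so no treatment effect no longer corresponds to observed survival. That is why it is not a valid RPSFT.

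**Illustration on the medians.** Medians do not add exactly, so this shows direction only. Take 12 months of AG-120 survival, 6 of them on drug, and a placebo target of 8:

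- General: 6 + 6·exp(ψ) = 8, so ψ = ln(2/6) = −1.10
- Start-to-death: 12·exp(ψ) = 8, so ψ = ln(8/12) = −0.41
- Dosing time only: 6·exp(ψ) = 8, so ψ = ln(8/6) = +0.29, the sign labelled harmful

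**Simulation.** There were 80,000 vs 40,000 subjects without censoring, placebo latent median 8 months, AG-120 duration median 6, and placebo progression median 3. Assumptions not in the documents are crossover in 50, 70 or 90% of progressing placebo subjects, median 3 or 6 months on AG-120 after crossover, and the true effect. The true effect was either a time ratio of 2.0 while on drug or 1.49 from start to death. The hazard ratio is taken as observed AG-120 survival against reconstructed placebo survival.

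| Configuration | General | Start-to-death | Dosing time only |
|---|---|---|---|
| On-drug ratio 2.0, 70% crossover, 6 months after crossover | 0.77 | 0.79 | 0.77 |
| Same, 3 months after crossover | 0.77 | 0.70 | 0.52 |
| Start-to-death ratio 1.49, 70% crossover, 6 months | 0.71 | 0.67 | 0.67 |
| Range over all configurations | 0.69-0.83 | 0.64-0.79 | 0.37-0.79 |

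In the first row ψ under dosing time only is +0.60 (time ratio 0.55), yet the hazard ratio shows benefit. The readings nearly agree when drug duration after crossover matches the AG-120 arm. They separate when it is shorter, because more of the crossed-over subjects' survival is then deleted.

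**A second set-up**, with 40-50% of AG-120-arm survival off drug and the same crossover and duration range, gave hazard ratios of 0.72-0.82 (general), 0.57-0.68 (start-to-death) and 0.37-0.61 (dosing time only). ψ under the last ran from −0.375 to +0.15. In simulated trials of 186 subjects cut at 150 deaths (3 months after crossover), the sign of ψ differed from the general formula in 4-29% of trials for dosing time only and 0-1% for start-to-death. The dosing-time hazard ratio was never above 1.

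**Re-censoring.** Under start-to-death, every AG-120-arm time is multiplied by the same factor, so not re-censoring that arm is sound. With a separate off-drug term, censoring on the U scale depends on how long each subject stayed on drug. That is the informative censoring which Appendix C sets out to avoid.

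**The case against.** The strongest reply is that Appendix C already means start-to-death. Placebo dosing also ends at progression (SAP Section 8), yet the line for placebo subjects who never cross over is T_pbo alone. If the superscripts meant dosing time, that line would delete survival too. The text describes a factor acting on survival time, and the no-re-censoring rule suits only this reading. All of this stands: the three lines form a coherent start-to-death model, and it is the definition of T_on that disagrees. But that definition is the only one given, and the arm lines are presented as its special cases.

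A reader might infer that the adjusted OS result could turn against AG-120. The documents do not support that. The reported quantity is a hazard ratio, and it stayed below 1 in every large-sample run. The sign change concerns ψ, and as a systematic effect it arises only under the dosing-time reading. In the 186-subject trials that reading and the general formula fell on opposite sides of 1 in 4-14% of cases, always with the general formula above 1 and dosing time below. The error therefore favours AG-120.

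Nor do all three lines lose time: the non-crossover line is complete, and the crossover line keeps survival before the switch. The log-rank wording is only an example and does not prescribe an unstratified test, and no size is claimed for stratification. Finally, subjects may stay on AG-120 after progression, so 6 months is only a stand-in for time on drug.

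**Conclusion.** The contradiction is real and needs correcting before the analysis is programmed. Applied as defined, the AG-120 and crossover lines discard observed survival. The adjusted hazard ratio was then 0.37-0.79, against 0.69-0.83 (general) and 0.64-0.79 (start-to-death). The difference is negligible when time on drug after crossover is similar to that in the AG-120 arm and clear when it is about half. These sizes rest on the assumed crossover rate, post-crossover duration and true effect, and on the absence of censoring. The internal contradiction rests on none of them.

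A reader might also take this as a threat to the trial's OS conclusion. It is not: the alpha-controlled OS test is the ITT stratified log-rank test, and RPSFT is a sensitivity analysis outside it.

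**What to change.** In SAP Appendix C:

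1. For the main RPSFT analysis, define T_on and T_ag120 as time from first AG-120 dose to death or censoring, and T_off and T_pbo as time before that dose. The three lines and the current re-censoring rule can then stay.
2. Add a sensitivity run in which T_on is actual time on AG-120, T_off includes time after AG-120 stops for every subject, and re-censoring is applied in both arms.
3. Name the log-rank test stratified by prior lines (1 vs 2) for the grid search in both runs, to match the primary OS test.

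The cost is about half a page of Appendix C and one extra program run.
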